The stroke survivor arm of this study will address the primary research question: 'Is an adapted Cognitive Stimulation Therapy intervention acceptable to pre-frail stroke survivors?'. Similarly, the informal carer arm will address the primary research question: 'Is an adapted Cognitive Stimulation Therapy intervention acceptable to the informal carers of pre-frail stroke survivors?'. These questions are important because, if the intervention were deemed unacceptable by either group then further adaptations, or a new intervention, will be required for use in the later feasibility trial of the full multicomponent intervention. Acceptability will be

operationalised in this study according to the Theoretical Framework of Acceptability (TFA) developed by Sekhon et al. (2017) which consists of seven constructs of acceptability (Appendix A).

Secondary research questions are: "How can the intervention be improved?", this question will help inform the development of the cognitive stimulation intervention adopted in the feasibility RCT; and "Is the intervention feasible to use in further research?", in particular, we are interested to find out if it is feasible to recruit and retain the required numbers to run the group intervention to inform the protocol of future research hoping to utilise this intervention.

Patient and Public Involvement

Patient and Public Involvement (PPI) was sought from a pre-frail stroke survivor and her IC (husband). Their input has been sought to determine the acceptability of recruitment materials (participant information sheets [PIS] and joint leaflet), as such we have adapted the PIS and joint leaflet to include careful consideration when explaining frailty, to be more friendly and gentle to lay-persons and reduce the use of the term, in an effort to move away from the negative connotations that the PPI members felt the term holds. We continue to discuss how to best adapt CST materials to be acceptable to stroke survivors, this has included a suggestion of music being played in the background to the group song to compensate for difficulties common in projecting one's voice after stroke.

Adaptation of CST Materials

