CST was developed by Spector et al. (2003) as a group intervention to help improve the cognition and quality of life in those with a diagnosis of dementia and was based on the theoretical concepts of reality orientation and cognitive stimulation. The intervention consists of 14 45-minute long sessions, recommended to be delivered twice per week for seven weeks. Each session is focused on a theme (e.g. food, sounds, faces and scenes) and contains

activities and discussion points designed to stimulate the use of memory and other cognitive skills (Spector et al., 2001). The CST manual (Spector et al., 2020) provides the theme for each session and suggests a choice of two activities relating to this theme.

Eight sessions of CST will be adapted for use in this pilot study. Adaptations have been, and will continue to be, made based on discussions with the PPI advisors and input from research team member, [name] (Principal Clinical Psychologist in Stroke at Addenbrooke's Hospital). Adaptations will consider the types of activities that are included within the sessions and the 'take home sheets' and how the original principles of CST can be maintained as much as possible whilst still allowing for changes that will make the intervention more suited for stroke patients, based on the existing evidence for psychological and cognitive interventions for stroke.

The 'take home sheets', will be sheets that are given out after each session for the stroke survivor to take home and will include some psychoeducation information along with some optional, additional activities that can be completed at home with the informal carer. This is not something suggested in the original CST manual but is instead informed by the later developed Individual Cognitive Simulation Therapy, or iCST. In iCST the intervention sessions are completed in the home setting and led by a carer and have been found to improve the quality of the caregiving relationship between a person with dementia and their carer (Orrell et al., 2017).

Consent has been gained from the developers of CST to adapt the materials for use in this novel context.

For the remainder of this protocol, the adapted CST intervention that is to be used in this research will be referred to as *stroke-adapted cognitive stimulation therapy* or sCST. A draft, example session plan for sCST can be found in Appendix B.

Method

Design

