This study will gather rich data on the acceptability of sCST for pre-frail stroke survivors to ascertain the suitability of the intervention for incorporation in the FIESTO feasibility RCT. As the study will examine the acceptability of the intervention prior to clinical trial, there will be no randomisation or control group, it is categorised as a non-randomised pilot study: a study in which “all or part of the intervention to be evaluated and other processes to be undertaken in a future trial are carried out without randomisation of participants” (Eldridge et al., 2016, p. 15).

This research will adopt a mixed methods design. Qualitative data will be collected via focus groups to gain a rich understanding of the acceptability of the intervention and how it could be changed and improved to best suit the needs and abilities of pre-frail stroke survivors from the perspective of both stroke survivors themselves and their informal carers. Descriptive quantitative data will also be collected from stroke survivors (not the informal carers) using the Theoretical Framework of Acceptability Questionnaire (Sekhon et al., 2022) to quantify acceptability, helping to highlight areas of strength or weakness in intervention acceptability. Data relating to recruitment success and group retention rates will also be collected and descriptively reported in order to determine the feasibility of recruiting participants to research using this intervention.

The philosophical stance, or paradigm, taken in this piece of research is that of pragmatism, where reality is socially constructed and, as such, it is unlikely that reality can ever be wholly understood. However, knowledge can be generated by understanding what practically works best (or doesn't work) within the specific context (Kaushik & Walsh, 2019). Due to its balanced position and practical approach, pragmatism is well suited to feasibility research (Johnson & Onwuegbuzie, 2004).

Participants

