Focus groups will be held via Microsoft Teams and will be recorded using the in-built record function so that they can be later transcribed ready for analysis. The groups will take place in the weeks soon after the last session of the intervention and will each last between one and two hours

The topic guides used for the informal carer and stroke survivor focus groups will each be based on the Theoretical Framework of Acceptability (TFA; Sekhon et al., 2017) and data will be analysed through framework analysis (FA) so that data can be mapped onto this pre-existing theoretical framework. The use of the TFA to inform a topic guide and to structure FA has been

shown an effective way of collecting and analysing qualitative data on pilot interventions for pre-frailty (Western et al., 2023). A draft version of the topic guide for stroke survivor participants can be found in Appendix D. Development of the topic guides is ongoing, as discussions with PPI volunteers continue.

Quantitative Data

Stroke survivor's perspectives of the acceptability of the intervention will also be assessed using a questionnaire measure adapted from the 'generic TFA questionnaire' (Sekhon et al., 2022; Appendix E), which was produced by the team who developed the TFA itself (Sekhon et al., 2017). From this, descriptive data (mean ratings for each acceptability construct) can be collected. This scale has been used in several other studies investigating the acceptability of a new intervention, including with populations of pre-frail older adult memory clinic patients (Western et al., 2023). This questionnaire will be conducted via a pseudonymised online form, using Microsoft Forms, and distributed by email after the last session of the sCST intervention is completed and will need to be completed prior to the focus group discussions. Participants may be prompted by a further email to complete the form if response numbers are lower than expected in the lead-up to the focus groups.

Where possible, researchers will also keep an anonymous record of the number of participants identified as being eligible for the research so that a recruitment success percentage can be calculated. A percentage will also be calculated for stroke survivor participant retention rates; in other words, how many participants remain in the intervention for the full eight sessions. This will help to assess the feasibility of recruiting participants to take part in this research that uses this sCST intervention.

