Appendix D

Example Focus Group Topic Guide (Draft)

Please note, this is a draft topic guide for the stroke survivor participants. Development of topic guides is ongoing, with input from PPI volunteers.

Research goals of the focus group:

- How would pre-frail stroke survivors feel about adapted CST as an intervention?
- What do pre-frail stroke survivors think about the amount of effort that would be required to participate in an adapted CST intervention?
- What, if any, ethical consequences did pre-frail stroke survivors feel there might be to engaging in an adapted CST intervention?
- What did pre-frail stroke survivors see as the potential costs of engaging in an adapted CST intervention?
- How effective do pre-frail stroke survivors think an adapted CST intervention could be?
- How confident do pre-frail stroke survivors feel about engaging in an adapted CST intervention?
- How well do pre-frail survivors understand the adapted CST intervention and how it works?

Introduction – approximately 10 minutes:

- *Welcome, introduction of the focus group*
- *Instructions regarding the focus group:* “I am interested in how you felt about the sample sessions of adapted CST that you tried and how you would feel about the idea of attending a full programme of perhaps 14 weekly sessions”
- *Ground rules:* “I will ask a number of questions, and I would like to hear from as many of you as possible for each question. It would be helpful for me if only one person speaks at a time so please wait until one person is finished before the

next person speaks. If you are able to use the 'hands up' button, it would be helpful if you can press this when you have something to say and I will then invite you to speak. Please be respectful of one another, every opinion is valid and helpful. Please be honest because your comments will help us to know what works well and what we might need to change in order to make it better. We will take a break half way through so you can go to the loo or get a drink, but if you need to step out at any point before or after this break please go ahead – just turn off your camera and microphone and turn them on again when you come back"

Main questions – approximately 90 minutes:

- "To start us off, could you please each tell me one word that you feel summarises what you thought of the eight sample sessions you had?"
- "Thank you, let's talk a bit more about how you felt about the sessions you tried"
 - What did you like about the sessions?

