 - What did you not like?
 - What did you find difficult about the sessions or the process of attending the sessions?
 - Did you find the activities enjoyable?
 - What did you think was the purpose of the activities? And do you think that the activities helped you in any way?
 - Did you gain anything from coming to these sessions?
 - Were there any negatives to coming to these sessions?
 - Did the sessions feel relevant to the difficulties you experience after your stroke?
 - Thinking back to before the sessions, how did you feel about attending the first one?

~Comfort break – 10 minutes~

- Now I would like to ask you a few questions about how you would feel about

attending a full course of sessions like these, perhaps 14 sessions once a week?

- Do you think there would be any benefits to attending a full course of this intervention? If so what do you think the benefits could be?
- (if not mentioned – do you think this intervention would have any effect on your ability to complete your usual day-to-day tasks/your mood/your memory and thinking skills?)
- Do you think a full course of this intervention would help you to achieve your goals?
- What would be the barriers or challenges involved in attending a full course of this intervention?

- Finally, I want to ask you about any changes or improvements that might be needed
 - Is there anything you would change about the general format of the sessions? (e.g. length, frequency, session structure)
 - Is there anything you would change to the content/themes of the sessions?
 - Is there anything missing that you feel would be helpful?
 - Is there anything you would change about the types of activities included in the sessions?

Conclusion – approximately 10 minutes:

- *Sum up what has been discussed, mention the positive aspects, compliment and thank the participants*
 - “Is there anything important to you we haven't mentioned?”
 - “If you want to follow any issues you have talked about, you can contact myself or my supervisor via email”
 - “We will shortly send you a debrief letter which will explain your options about withdrawing from the study, raising concerns, and how you can be updated on the results of the study. You will also receive a £10 shopping voucher.”

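### Does the acceptability conclusion cover the eight sessions delivered, or the longer course that the draft topic guide asks about?

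*Combined protocol and SAP*

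**What the plan says.** Adaptation of CST Materials describes original CST as 14 sessions of 45 minutes, recommended twice a week for seven weeks. For this study, "Eight sessions of CST will be adapted for use in this pilot study". The same section closes by naming the product: "the adapted CST intervention that is to be used in this research will be referred to as" sCST. Procedure delivers two 45-minute sessions at each weekly visit for four weeks.

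Quantitative Data defines retention as "how many participants remain in the intervention for the full eight sessions".

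Design says that data on the acceptability of sCST are gathered "to ascertain the suitability of the intervention for incorporation in the FIESTO feasibility RCT". It classes the study as a non-randomised pilot, using a published definition under which "all or part of the intervention to be evaluated" may be carried out. Research questions states the consequence of a finding of unacceptability by either group: "further adaptations, or a new intervention, will be required for use in the later feasibility trial".

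The draft survivor guide in Appendix D uses different language. Its introduction asks "how you felt about the sample sessions of adapted CST that you tried" and then about a longer programme. After the comfort break the lead question concerns "attending a full course of sessions like these, perhaps 14 sessions once a week".

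**The concern.** Set next to each other, the body and the guide appear to name two different interventions. Under Quantitative Data, a participant who stays for eight sessions has completed the intervention; under Appendix D the same participant has only tried it. The pilot definition quoted in Design admits both readings, and the protocol does not say in terms which one applies.

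The distinction could matter. Burden and opportunity cost are two of the seven acceptability constructs, and both plausibly depend on how long a course lasts. If the FIESTO trial adopted a longer course, favourable ratings of four visits might be read as support for something nobody had attended. The only evidence on the longer course would then be a few answers to hypothetical questions. The guide's research goals add to the impression: five of the seven are worded prospectively, whereas most items in the generic questionnaire (Appendix E) look back.

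**Working it through.** **The delivered schedule reproduces.** Inputs: two sessions per weekly visit, four weeks, 45 minutes each (Procedure).

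- Sessions: 2 × 4 = 8, as stated.
- Original CST (Adaptation of CST Materials): 2 × 7 = 14, as stated.
- Delivered session time: 8 × 45 / 60 = 6.0 hours, in 4 visits.

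**The course in the guide.** Inputs: 14 sessions, once a week (Appendix D). The guide gives no session length, so this is an assumption.

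- Visits: 14, and 14 / 4 = 3.5 times the pilot.
- Session time at 45 minutes each, which matches the guide's own count of eight sessions: 14 × 45 / 60 = 10.5 hours, and 10.5 / 6.0 = 1.75 times the pilot.
- If each weekly session were instead a two-part visit as in the pilot: 14 × 90 / 60 = 21 hours, or 3.5 times.
- Share delivered: 8 / 14 = 57%.

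The two formats therefore differ materially. The remaining question is whether any result could be attributed to the wrong one.

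**What each data source refers to.**

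| Source | Refers to | Basis |
|---|---|---|
| Retention percentage | Eight sessions | Its definition in Quantitative Data |
| Questionnaire means | Sessions attended | Sent after the last session and completed before the focus groups; the longer course appears only in the focus-group guide |
| Guide, before the break | Sessions attended | Nine prompts on the sessions tried |
| Guide, after the break, first block | Longer course | Lead question plus prompts on benefits, effects, goals and barriers |
| Guide, after the break, second block | Possible changes | Four prompts, including length and frequency |

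With both alternatives kept for two constructs (Analysis), the questionnaire has 10 items. In the generic version, 7 are in the past or perfect tense: liking, comfort, effort, effectiveness, confidence, opportunity cost and general acceptability. The other 3 are in the present: fairness, moral consequences and coherence. None mentions a course length. The study uses an adapted version, so this count describes the template only. The five prospective research goals likewise speak of adapted CST in general and name no course length.

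**What the conclusion refers to.** In the Design sentence, the intervention whose suitability is judged is sCST, named earlier in the same sentence. sCST was defined as the adapted intervention used in this research, and eight sessions are what this research adapts and delivers. No passage in the body describes a longer sCST.

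**What the full-course questions are for.** Research questions includes a secondary question on how the intervention can be improved, meant to inform the version taken into the feasibility trial. Asking for views on a longer format serves that question.

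**What the ratings can trigger.** Further adaptation follows if either survivors or carers find the intervention unacceptable. Carers complete no questionnaire, and Design gives the survivor ratings a descriptive role. No passage lets a mean rating decide the matter alone.

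**The case for a change.** The best case for a change runs as follows. The phrase used in the guide, a full course of this intervention, contradicts the reading that eight sessions are the intervention. Its 14 sessions match the original CST count, but its weekly frequency matches neither original CST nor the pilot, so the intended course cannot be inferred. Appendix A separates anticipated from experienced burden, opportunity cost and effectiveness, yet Analysis does not say that views on delivered and hypothetical sessions will be reported apart. One or two sentences would settle it, and the guide is still open to edits.

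Part of this stands. The guide's labels do conflict with Adaptation of CST Materials, Quantitative Data and Procedure, and those passages must be reconciled. The word session is also used loosely: Procedure applies it both to a 45-minute unit and to a weekly visit, while Reimbursement and Coercion speaks of visits. Both are matters of wording.

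The rest does not carry the point further. Analysts coding to a framework that already distinguishes anticipated from experienced constructs, with transcripts in which the two formats are taken up in turn, have what they need to keep them apart. That the guide's course is only tentatively specified fits its use as a prompt for discussion. Piloting part of an intervention, and asking participants about a longer one, are both legitimate in a study of this kind.

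**Conclusion.** The inconsistency is one of labelling in a draft appendix, and no change to the plan follows. Read with its own definition of sCST, the protocol already ties the suitability aim to the eight delivered sessions. The retention percentage and the questionnaire means are correct for those sessions whichever course the later trial adopts. The full-course answers inform the secondary question on improvement. There is no hypothesis test or formal sample-size calculation for the ambiguity to disturb, and spelling out the scope would change no estimate, analysis or data item.

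The gap between formats is not trivial: 4 visits against 14, and 6 hours against 10.5 hours at 45 minutes a session (21 hours if each were a two-part visit). A write-up should therefore not carry four-week ratings or retention over to a longer course. That is ordinary care in reporting.

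This rests on three assumptions: the final guide keeps questions on sessions attended apart from those on a longer course; the adapted questionnaire still asks about what was attended; and the carer guide, which the documents do not show, is built along similar lines. The protocol says that the guides are still being developed, which is the natural point to bring their wording into line with the body. Nothing here favours one schedule over another.

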tabularising and rearranging according to thematic content in summary form. The final stage will involve mapping and interpretation to explore the relationships between the concepts connecting the TFA with the charted data; an example of this is found in Western et al.'s (2023) study on an intervention for pre-frail individuals. Some 'open coding' will also be carried out to ensure no important data are missed from the analysis (Gale et al., 2013).

In terms of quantitative data obtained from the stroke survivor participants, the degree of acceptability will be calculated by calculating the mean ratings for responses to each of the seven TFA constructs on the acceptability questionnaire measure, the mean rating for the general acceptability item (item 10), and the total mean rating of all items. For two of the seven constructs, Sekhon et al., (2022) suggest a choice of two questions, whereas all other constructs have only one question. For these two constructs, it has been decided that both of the suggested questions would be included in the acceptability questionnaire used in this study, as it was felt that the questions were different enough from one another that they would both be helpful to ask. For example, the generic TFA questionnaire suggests either 'How fair is [Intervention] for [people/ participants/ recipients] with [condition]?' or 'There are moral or ethical consequences [behaviour *i.e. to engage with*] [intervention]' as questions to measure the construct of ethicality.

To improve the sensitivity to context (Yardley, 2000) the researchers will keep reflective diaries of the data analysis process to ensure that consideration is taken of their role in the research and the analysis and to increase awareness of how this, as well as their existing knowledge, experiences and assumptions, may influence the analysis.

References

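### The draft stroke survivor focus-group guide has the moderator recap only the positives just before the final open question, which may discourage late criticism at that one question

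*Combined protocol and SAP*

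**What the plan says.** Appendix D sets out the script for the stroke survivor focus groups and states its status: "Please note, this is a draft topic guide for the stroke survivor participants". The informal carers have a separate guide, which is not shown.

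The script has an introduction of about 10 minutes, then "Main questions – approximately 90 minutes", a 10-minute comfort break within the questions, and "Conclusion – approximately 10 minutes". The ground rules in the introduction ask for candour: "Please be honest because your comments will help us to know what works well and what we might need to change". The main questions include direct requests for criticism, for example "What did you not like".

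The Conclusion opens with an instruction to the moderator: "Sum up what has been discussed, mention the positive aspects, compliment and thank the participants". Beneath it comes the last open question: "Is there anything important to you we haven't mentioned". The script then invites participants to follow up issues by email and tells them that a debrief letter will explain how to raise concerns.

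Under Quantitative Data, the survivors' acceptability questionnaire has to be completed before the focus groups. Under Analysis, "the researchers will keep reflective diaries of the data analysis process", and the same sentence says that these are to prompt consideration of the researchers' part in the research as well as in the analysis.

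**The concern.** Acceptability to survivors is the primary question of the survivor arm (Research questions). The focus groups supply its qualitative evidence, which is meant to inform whether the adapted therapy suits the later FIESTO feasibility trial (Design). The secondary question, how the intervention can be improved, depends on participants voicing criticism.

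A recap by the researcher tells the group what was heard and valued. If it singles out positives and comes just before the final invitation to add anything, a participant with an unspoken reservation has a mild cue to leave it unsaid. The opposite cue is not scripted, so any influence runs towards a favourable result.

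The setting makes some courtesy plausible already. Recruitment is through a stroke service in which two members of the research team work (Participants), and a hospital medic attends the sessions (Harm, Burden and Benefits).

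The closing question also has work to do. Appendix D lists perceived ethical consequences and confidence in engaging among the research goals of the group, but no scripted prompt asks about either directly. The nearest prompt to confidence asks how participants felt before the first session. Views on these two constructs may therefore surface only if someone volunteers them.

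**Working it through.** No statistical formula applies. The plan has no error rate, margin or effect size that depends on this step, and it gives no figure to reproduce. The check is to read the script in order, count what comes before and after the instruction, and ask which data it can reach.

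**Prompts before the Conclusion** (each bulleted question counted once, lead-in lines not counted):
- Opening one-word summary: 1
- Sessions tried: 9
- A full course: 4
- Changes and improvements: 4
- Total: 1 + 9 + 4 + 4 = 18

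**Prompts that invite criticism or change:**
- Sessions tried: 3 (dislikes, difficulties, negatives)
- A full course: 1 (barriers or challenges)
- Changes and improvements: 4 (format, content, anything missing, activity types)
- Total: 3 + 1 + 4 = 8 of 18

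**Open questions after the instruction:** 1.

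**Time.** The scripted blocks total 10 + 90 + 10 = 110 minutes. The Conclusion is 10/110 = 9% of that, or 10/120 = 8% if the 10-minute break is added.

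**Which data the instruction can reach:**
- Answers to the 18 earlier prompts: none, because they are already recorded.
- Questionnaire ratings: none, because the form is completed before the groups meet.
- Carer groups: unknown, because their guide is not shown.
- The closing question in the survivor groups: yes. Two of the four planned groups, five survivors each, give 2 × 5 = 10 people at most. Ten are recruited to allow for drop-out, so fewer may attend.

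**Wording.** The instruction names positives and has no counterpart for negatives or proposed changes. No line asks participants to confirm the summary. The one-sidedness is therefore written into the script and is not merely a missing detail.

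**The case against.** The strongest reply is that the instruction comes too late and is too slight to matter. Criticism has been sought for about 90 minutes, honesty was requested at the start, and survivors who leave the intervention may still attend to give feedback. Summing up what was discussed would naturally include criticisms. Placed beside the compliment and thanks, the reference to positives may be a courtesy about the discussion and not praise of the therapy. The groups are semi-structured, so the order of recap then question is read from the layout and not stated as a rule. The documents do not say who moderates. The guide is a draft still being developed with patient and public involvement.

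Most of this stands, and it limits the point to one question. It does not remove it. The ambiguity leaves a moderator free to praise the therapy, and draft status makes this the easiest time to edit.

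A reader might infer more than the documents support:
- *That the acceptability data as a whole are biased.* The counts above rule this out for everything recorded before the Conclusion.
- *That the closing question is the only unprompted one, or the last chance to speak.* The one-word opener is also open and is put to everyone, and email and the debrief letter offer later routes. Those later routes may not enter the transcript.
- *That the two uncovered constructs go unmeasured.* The source questionnaire in Appendix E has items on ethicality and self-efficacy. What could be lost is participants' own account of them.
- *That reflexivity is confined to analysis.* The diaries are described as being of the analysis process, but their stated purpose also covers the researchers' role in the research. Requiring further entries would add little.

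**Conclusion.** The point holds in a narrow form. The script contains a one-sided closing instruction directly before the final open question, and this may discourage late criticism there, in the two survivor groups. Any effect would be in the favourable direction. Its occurrence and size cannot be established from the documents.

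This rests on three assumptions: that moderators follow the order as laid out, that they read the reference to positives as including the intervention, and that the final guide keeps the draft wording. If any of these fails, the concern shrinks or disappears.

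The carer groups deserve a check because carers complete no questionnaire, so the focus groups are their only acceptability data. Nothing shown establishes that their guide has the same closing. Overall this is a minor, cheap improvement and not a flaw that threatens the study's conclusions.

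**What to change.** Reorder and reword the Conclusion of the survivor guide:

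1. Before any recap, put the open question, extended to invite both kinds of comment, for example: *Is there anything else that matters to you, good or bad, that has not come up?*
2. Replace the instruction on positive aspects with a brief balanced summary of what people liked, what they disliked and what they would change.
3. Ask whether the summary is accurate and whether anything is missing.
4. Then thank participants.

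Check that the carer guide closes in the same way.

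The cost is an edit to a draft and a minute or two within the 10-minute Conclusion, with no extra staff. Time is tight if the break is additional to the other blocks, because the script then totals 110 + 10 = 120 minutes against the two-hour upper limit under Procedure. The recap should therefore be kept short.
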